6.1 PRESTUDY AND CONCOMITANT THERAPY

Concomitant medications will be documented during screening and during the study.

6.2 MONITORING TREATMENT COMPLIANCE

Johnson & Johnson Vision Care, Inc. representatives or designees will monitor the study in a manner consistent with ICH GCP E6. The study monitors will maintain close contact with the Principal Investigator and the Investigator's designated staff. The monitor's responsibilities will include:

- Ensuring that the investigation is being conducted according to the protocol
- Ensuring the rights and well being of subjects are protected
- Ensuring that protocol deviations are documented with corrective action plans, as applicable
- Ensuring that the site has sufficient test article and supplies
- Clarifying questions regarding the study
- Resolving study issues or problems that may arise
- Reviewing the study records to ensure completeness and accuracy
- Study and subject source document records reviewed will include:
 - The Information and Consent Form per 21CFR Parts 50 and 56 and the Data Protection Act
 - Source documentation including consenting, medical history, concomitant medications, and adverse event information as applicable. The source document should be initialed and dated by the study investigator/s.
 - Investigational product shipping, dispensing, accountability, and return/destruction records
 - Study related Regulatory documents as per ICH E3 section 8

6.2.1 MONITORING PLAN

This section of the protocol constitutes the monitoring plan for this study:

At least two monitoring visits will be completed during the study. A combined interim and closure visit may be conducted.

The following data will be reviewed:

1. Incl/Exc-Eligibility
2. Med History
3. Con Meds
4. Demographics
5. Test Article Accountability
6. Test Article Information
7. Primary End Points (PEP)
8. Secondary End Points
9. Protocol Deviations (PD)
10. AE's

11. Product Quality Complaints
12. Compliance
13. Symptoms
14. Comments
15. Intentionally Left Blank (ILB)
16. Unscheduled Visits (UV)
17. Final Evaluation

6.3 UNSCHEDULED VISITS

If, during the investigation, a subject experiences any investigational device-related difficulties and/or problems requiring an unscheduled visit to the clinic, the following information will be collected at a minimum:

- Chief complaint prompting the visit. If the reason is an adverse event, the applicable eCRF for the adverse event should be completed and source documentation completed as appropriate.
- Date and time of the visit and all procedures completed at the unscheduled visit
- Review of adverse event and concomitant medications
- Documentation of any investigational product dispensed or collected from the subject.
- Slit lamp findings (using the Slit Lamp Classification Scale)

If the Investigator withdraws a subject from the study, the final study visit case report forms must be completed indicating the reason(s) why the subject was withdrawn. The subject enrollment log should be completed documenting the date and primary reason for withdrawal and the study CRA notified.

Any investigational device-related difficulties and/or problems that are ongoing at the time of the final study visit will be followed by the Investigator, within licensure, until they have returned to pre-treatment status, stabilized, or been satisfactorily explained. If further treatment (i.e., beyond licensure) is required, the subject will be referred to the appropriate health care provider.

7.1 EFFICACY PARAMETERS

The primary efficacy parameters for this study will be measurements of binocular functional visual performance under distance day time conditions (250 cd/m²) for centrally presented high contrasts (HC) time controlled visual acuity (TCVA) targets.

The secondary efficacy parameters for this study will be measurements of binocular functional visual performance of the test and control contact lenses for the following conditions:

- i. Distance night time conditions (2.5 cd/m²) for centrally presented HC TCVA targets;
- ii. Intermediate vision indoor conditions (50cd/m²) for centrally presented HC TCVA targets.

Other efficacy parameters for this study will be measurements of:

- i. Monocular functional visual performance for centrally presented high contrast (HC) time controlled visual acuity (TCVA) targets.
 - a. Distance day time conditions (250 cd/m²)
 - b. Distance night time conditions (2.5 cd/m²)
 - c. Intermediate vision indoor conditions (50cd/m²)
- ii. Distance monocular and binocular functional visual performance of the test and control contact lenses under night time conditions (2.5 cd/m²) for HC TCVA targets presented at 5° eccentricity;

- iii. Intermediate vision monocular and binocular functional visual performance of the test and control contact lenses under indoor conditions (50cd/m²) for HC TCVA targets presented at 5° eccentricity;
- iv. Distance monocular and binocular functional visual performance of the test and control contact lenses under night time conditions (2.5 cd/m²) for decreasing contrast targets presented at 20° eccentricity;
- v. Intermediate vision monocular and binocular functional visual performance of the test and control contact lenses under indoor conditions (50cd/m²) for decreasing contrast targets presented at 20° eccentricity.
- vi. Horizontal binocular visual field;
- vii. Horizontal monocular visual field.
- viii. Subjective rating of performance following driving simulation while wearing test and control contact lenses under night time condition (e.g. City Car Driving Simulator / PC game);
- ix. Subjective rating of performance following PC based reaction time game while wearing test and control contact lenses.

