3.1 DESCRIPTION OF OBJECTIVES AND PURPOSE

Johnson & Johnson Vision Care (JJVCI) are interested in evaluating the effects of incorporating a black annulus within a hydrogel contact lens, on functional visual performance. The black annulus is designed to mimic the performance of a similar design. The research aims to determine whether this black annulus is likely to have any detrimental effect on vision for the wearer. This pilot study will compare the central and peripheral visual performance, including functional assessment of vision, of a test contact lens incorporating a black annulus with that of a control clear contact lens.

The primary objective of the study will be to measure the binocular functional visual performance of the test and control contact lenses under distance day time conditions (250 cd/m²) for centrally presented high contrasts (HC) time controlled visual acuity (TCVA) targets.

The secondary objectives of the study will be to measure the binocular functional visual performance of the test and control contact lenses for the following conditions:

- i. Distance night time conditions (2.5 cd/m²) for centrally presented HC TCVA targets;
- ii. Intermediate vision indoor conditions (50cd/m²) for centrally presented HC TCVA targets.

The additional study measurements will be:

- i. Monocular functional visual performance for centrally presented high contrast (HC) time controlled visual acuity (TCVA) targets.
 - a. Distance day time conditions (250 cd/m²)
 - b. Distance night time conditions (2.5 cd/m²)
 - c. Intermediate vision indoor conditions (50cd/m²)
- ii. Distance monocular and binocular functional visual performance of the test and control contact lenses under night time conditions (2.5 cd/m²) for HC TCVA targets presented at 5° eccentricity;
- iii. Intermediate vision monocular and binocular functional visual performance of the test and control contact lenses under indoor conditions (50cd/m²) for HC TCVA targets presented at 5° eccentricity;
- iv. Distance monocular and binocular functional visual performance of the test and control contact lenses under night time conditions (2.5 cd/m²) for decreasing contrast targets presented at 20° eccentricity;
- v. Intermediate vision monocular and binocular functional visual performance of the test and control contact lenses under indoor conditions (50cd/m²) for decreasing contrast targets presented at 10° eccentricity.

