7.2 METHODS FOR ASSESSING, RECORDING, AND ANALYZING EFFICACY

See detailed study procedures in section 4.7 regarding methods for assessing and recording efficacy. Statistical methods for analyzing efficacy data are provided in section 9.1 below.

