9.1 STATISTICAL METHODS TO BE EMPLOYED

All data summaries and statistical analyses will be performed using either the SAS software Version 9.4 or higher (SAS Institute, Cary, NC) or SPSS software Version 23.0 or higher (IBM Corp, Armonk, NY).

Description of Summary Tables

Summary tables (Descriptive statistics and/or frequency tables) will be provided for all baseline, efficacy and safety variables for each subject/eye as appropriate. Continuous variables will be summarized with descriptive statistics (n, mean, standard deviation (SD), median, minimum and maximum). Frequency count and percentage of subjects or eyes within each category will be provided for categorical variables.

Summaries will be presented by study lens type and will be performed separately by study population defined in section 9.7. Efficacy variables will be summarized descriptively on both the analysis and safety population. Safety variables will be summarized descriptively for the safety population. Unscheduled visits will be summarized separately if applicable. If the difference between the analysis and safety population is higher than 15%, a sensitivity analysis will be conducted on the safety population.

Data summarization will be performed by OTG-i, with oversight by the JJVCI study responsible biostatistician.

Raw data will be provided to OTG-i by JJVCI/Bioclinica in the Study Data Tabulation Model (SDTM) format in conformance to Clinical Data Interchange Standards Consortium (CDISC) standards. OTG-i will be responsible to create CDISC Analysis Data Model (ADaM) datasets as well as the display outputs including tables, listings and figures (TLFs) based on the CDISC ADaM datasets. For more details about CDISC, SDTM and ADaM, please refer to www.cdisc.org.

OTG-i shall follow specifications of ADaM datasets and mock shells of TLFs provided by JJVCI. Sample datasets, ADaM specifications, and mock shells of TLFs may be provided to OTG-i by JJVCI midway through the study if needed.

Description of Analysis Methods

Efficacy Analysis Set

The primary and secondary analysis will be performed on all randomized subjects who successfully completed the study without any protocol deviations that the study responsible clinician documents as impacting the assessment of the hypotheses (i.e. analysis population). Justification of excluding subjects with protocol deviations in the analysis population set will be documented.

Analysis Methods

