The binocular central distance high contrast, high illumination (250 cd/m²) TCVA, the binocular central distance high contrast, low illumination (2.5 cd/m²) TCVA and the binocular central intermediate vision high contrast, medium illumination (50 cd/m²) TCVA will be analyzed together using a linear mixed model. The model will include the experimental design factors: sequence of lens wear, period, lens type, condition (determined jointly by distance, illumination and eccentricity) as well as lens type by condition interaction as fixed effects; and subject as a random effect. Other baseline characteristics known of importance such as age, gender and race may be included as fixed covariates when appropriate. The covariance between residual errors from the same subject and period at different conditions will be selected based on the finite-sample corrected Akaike's Information Criterion (Keselman et al., 1998). Covariance structures considered may include:

- Variance Component (VC)
- Homogenous Compound Symmetry (CS),
- Heterogeneous Compound Symmetry (CSH),
- Heterogeneous Variance Component (UN(1))
- Unstructured Covariance Structure (UN).

For UN(1) covariance structures, condition nested within subject and period will be included as an additional random effect. For the remaining structures only subject will be included as a random effect. The improved Kenward and Roger method (Kenward and Roger, 2009) using the KENWARDROGER2 option will be used for the calculation of the denominator degrees of freedom. Heterogeneous models between the study lenses may be considered when appropriate. The log-likelihood ratio test will be used to test for homogeneity of variances between lens types.

Primary Hypothesis Testing:

The null and alternative hypotheses for non-inferiority in the binocular central distance high contrast high illumination TCVA are as follows: $H_0: \mu_1 - \mu_2 \leq -0.5$ v.s. $H_a: \mu_1 - \mu_2 > -0.5$, where μ_1 and μ_2 are the population mean of binocular central distance high contrast high illumination TCVA for the Test lens and the Control lens, respectively. Comparisons between the Test lens and Control lens will be conducted using two-sided 95% confidence intervals constructed for least-square means (LSM) difference (Test - Control) at central distance high contrast high illumination. Non-inferiority will be concluded if the lower limit of the LSM difference is greater than -0.5 VA units.

Secondary Hypothesis Testing:

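### Outside the three binocular central acuity endpoints, section 9.1 plans no within-subject lens difference or interval, although section 3.1 promises a comparison of peripheral and functional vision

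*Combined protocol and SAP*

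**What the plan says.** Section 3.1 sets the aim of finding out whether the black annulus harms the wearer's vision, and says: "This pilot study will compare the central and peripheral visual performance, including functional assessment of vision". Section 7.1 then introduces a third tier of outcomes with "Other efficacy parameters for this study will be measurements of". These are monocular central acuity at three luminances, targets at 5 degrees and further out, horizontal visual fields, and subjective ratings after a driving simulation and a reaction-time game.

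Section 7.2 refers the reader on: "Statistical methods for analyzing efficacy data are provided in section 9.1 below". Section 9.1 contains two relevant provisions.

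- General summaries. "Efficacy variables will be summarized descriptively on both the analysis and safety population". The content is given as "Continuous variables will be summarized with descriptive statistics (n, mean, standard deviation (SD), median, minimum and maximum"), with counts and percentages for categorical variables. The layout is "Summaries will be presented by study lens type and will be performed separately by study population defined in section 9.7".
- A crossover model. The three binocular central acuity endpoints (250, 2.5 and 50 cd/m²) "will be analyzed together using a linear mixed model" with sequence, period, lens type, condition and lens-by-condition as fixed effects and subject as a random effect. Two-sided 95% intervals for Test minus Control are specified for these three only.

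Section 9.1 also allows further exploratory analysis if the responsible clinician sees a need. It names no method for this.

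**The concern.** The study is a 2x2 crossover, so each subject is his or her own control and the natural estimate is the within-subject lens difference. Section 9.1 uses that structure for three endpoints and drops it from the planned output for the rest. A table of mean and SD per lens gives no SE or interval for the difference, and those are what a reader needs to judge whether an observed off-axis change is noise.

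At stake is the peripheral and functional half of the comparison announced in section 3.1. In a study looking for detriment, a reader who falls back on the two by-lens SDs will usually see less precision than the data contain, and may dismiss a real off-axis loss.

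**Working it through.** **Scope.** Section 4.7.1 (Visits 2 and 3, step 13) lists seven acuity or target conditions, four of them off-axis, each measured monocularly and binocularly: 7 × 2 = 14 combinations. The model covers 3, which leaves 14 − 3 = 11 without a planned lens contrast. The Esterman fields (right eye, left eye, both) and the two sets of ratings are also outside it. The model's condition factor is described as "condition (determined jointly by distance, illumination and eccentricity"), but all three modelled conditions are central. Eccentricity therefore does not vary, and no peripheral data enter.

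**Inputs.** n = 20 completers (section 9.2). Sequences are allocated 1:1 in blocks of two (section 4.5). The documents give neither an SD nor a within-subject correlation ρ, and the sample size has no power calculation, so there is no plan figure to reproduce. I assume equal SD s for the two lenses and take ρ at 0.5, 0.7 and 0.8.

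**Standard errors.** Unpaired: √(2s²/n). Paired: √(2s²(1−ρ)/n). Ratio: 1/√(1−ρ), which is 1.41, 1.83 and 2.24.

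**95% interval half-widths at n = 20.** Unpaired, from by-lens SDs: t(0.975, 38) × s × √(2/20) = 0.64 s at any ρ. Paired crossover: t(0.975, 18) × s × √(2(1−ρ)/20).

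| Assumed ρ | Unpaired | Paired | Width ratio | SE ratio |
|---|---|---|---|---|
| 0.5 | 0.64 s | 0.47 s | 1.36 | 1.41 |
| 0.7 | 0.64 s | 0.36 s | 1.76 | 1.83 |
| 0.8 | 0.64 s | 0.30 s | 2.15 | 2.24 |

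The width ratio is a little below the SE ratio because the unpaired interval uses 38 degrees of freedom and the paired one 18.

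**Coverage.** In a simulation of 20,000 trials with no period effect, the nominal 95% unpaired interval covered 99.2% at ρ = 0.5 and 99.9% at ρ = 0.7. The paired interval covered about 95%.

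**Point estimate.** With both values present for every subject, the difference of the two lens means equals the mean of the within-subject differences. So the crude estimate is recoverable and only its precision is lost.

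**Period.** If n₁ completers follow Test/Control and n₂ follow Control/Test, the crude difference carries (n₂ − n₁)/(n₁ + n₂) of any additive period effect. That is 0 at 10/10, 0.1 at 9/11 and −0.2 at 12/8.

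**The case against.** The strongest reply is that descriptive handling fits the rank of these outcomes. Sections 1.8, 3.1 and 4.1 treat them as additional or other observations in a pilot, with no hypothesis or margin, and the formal objectives are worded as measuring, not comparing. This stands as a reason not to test them. It does not explain why the descriptive output leaves out the paired difference. Sections 4.1 and 9.2 call the primary and secondary hypotheses exploratory too, yet those receive paired intervals.

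A reader might infer that no lens difference is available for the periphery. That goes too far. The analysis population has completed all visits, so subtracting the planned means gives the crude paired estimate wherever both values are present. The caveat applies to the safety population, where efficacy is also summarised. Section 9.5 rules out imputation, so the two lens means there may come from different subjects.

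A reader might also infer that the missing period adjustment biases the results. Blocks of two keep the randomised sequences almost equal, so bias needs unequal loss between sequences.

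Nor does the plan propose an unpaired interval. The width ratios describe what a reader could build from the tables, not a planned error.

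Finally, section 9.1 refers to sponsor-supplied table shells that are not in the documents, and these might include differences. The exploratory clause might produce them as well. Neither commits the trial to a paired estimate.

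**Conclusion.** The point holds as a limited gap in the planned output. Section 3.1 announces a comparison of central and peripheral vision, including functional assessment. Section 9.1 provides a within-subject estimate with an interval for 3 of 14 acuity or target combinations, and for none of the field or rating outcomes. Monocular central acuity falls outside the model as well, so the gap is not confined to the periphery.

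The size depends on the assumed correlation. A reader working from the by-lens SDs at n = 20 would get an interval about 1.36 to 2.15 times too wide for ρ between 0.5 and 0.8, assuming equal SDs and complete pairs. Period imbalance adds to this only if completers are unequal between sequences.

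The documents do not support saying that the peripheral aim goes wholly unanswered. What the plan lacks is a committed estimate with valid precision. This is a worthwhile improvement and does not threaten the primary analysis.

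**What to change.** In section 9.1, add the following, all labelled exploratory, with no test and no margin.

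- Monocular central acuity and the eccentric targets: the period-adjusted Test minus Control difference with a 95% interval, from a model with sequence, period, lens and random subject, fitted separately by condition and by eye or viewing mode. State the score scale for the decreasing-contrast targets, which the visible text leaves to the Manual of Procedures.
- Esterman scores and subjective ratings: the distribution of within-subject differences, with a median difference and a nonparametric interval where scores are bounded or skewed. A Gaussian model may not suit these.

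No new data or visits are needed. The cost is programming and tables for at least 11 model-based intervals (3 monocular central, 4 at 5 degrees, 4 decreasing-contrast), plus the field and rating summaries. None is adjusted for multiplicity, which agrees with section 9.3.

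Before the tables are specified, reconcile one inconsistency. Section 7.1 item v puts the intermediate decreasing-contrast target at 20 degrees, while sections 1.8, 3.1, 4.1 and 4.7.1 put it at 10.

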7.2 METHODS FOR ASSESSING, RECORDING, AND ANALYZING EFFICACY

See detailed study procedures in section 4.7 regarding methods for assessing and recording efficacy. Statistical methods for analyzing efficacy data are provided in section 9.1 below.

8.1 SAFETY PARAMETERS

The following safety parameters will be monitored and evaluated:

- Ocular physiology characteristics
- Lens fitting characteristics
- Adverse events
- Ocular symptoms
- Snellen distance visual acuity
- Reasons for discontinuation
- Reasons for unplanned lens replacement
- Quality Complaints

Safety parameters will be tabulated using frequency distribution tables and descriptive statistics. Adverse events will be listed by subject/eye. There will be separate summary tables for adverse events and infiltrative adverse events. Statistical methods for analyzing safety data, if any, are provided in section 9.

8.2 ADVERSE EVENTS

All adverse events will be recorded in the subject's source document and documented in the appropriate section of the subject's Case Report Form (CRF).

In conjunction with the medical monitor, the Investigator will evaluate adverse events to ensure the events are categorized correctly. Elements of categorization will include:

- Seriousness (see definition in Section 8.4).
- Expectedness – i.e. if the event was unexpected or unanticipated in that it was not previously identified in nature, severity, or degree of incidence (see definition in Section 8.4).

- Causality or Relatedness – i.e. the relationship between the test article and the adverse event (not related; doubtful; possible; probable; very likely - see definition in Section 8.4).
- Adverse Event Intensity or Classification – Adverse event intensity is used to assess the degree of intensity of the adverse event (mild, moderate, severe for all events). In addition adverse event Classification is used to assess the severity of ocular adverse events (AE not requiring treatment, non-significant or significant see definition in Section 8.4).
- Outcome – Resolved, ongoing, not resolved, resolved with sequelae, fatal, resolving, and unknown.
- Actions Taken – None, temporarily discontinued, permanently discontinued, other action taken.

In addition, a written report will be submitted by the Principal Investigator to the IRB/IEC according to their requirements. Such a report should comment whether or not the adverse event was considered to be related to the test article.

Non-Serious Adverse Events:

All non-serious adverse events, including non-serious adverse device effects, will be reported to the sponsor by the Investigator no later than 2 days from discovery for review by the Medical Monitor.

Serious Adverse Events:

The Investigator will inform the sponsor of all serious adverse events occurring during the study period as soon as possible by e-mail, fax, or telephone, but no later than 24 hours following discovery of the event. The investigator is obligated to pursue and obtain information requested by the Sponsor in addition to that information reported on the CRF. All subjects experiencing a serious adverse event must be followed up and all outcomes must be reported.

In the event of a serious adverse event, the investigator must:

- Notify the Sponsor immediately
- Obtain and maintain in the subject’s file all pertinent medical records, information and medical judgment for colleagues who assisted in the treatment and follow-up of the subject
- Provide the Sponsor with a complete case history which includes a statement as to whether the event was or was not related to the use of the investigational test article
- Notify the IRB/IEC as required by the IRB/IEC reporting procedure according to national regulations

Unanticipated (Serious) Adverse Device Effect (UADE):

In the event of an Unanticipated (Serious) Adverse Device Effect (UADE), the Investigator will submit a report of the UADE to the Sponsor and IRB/IEC as soon as possible, but no later than 24 hours after the Investigator first learns of the effect. This report is in addition to the immediate notification mentioned above.

The Sponsor must conduct an evaluation of the UADE and must report the results of the evaluation to FDA, the IRB/IEC and participating investigators within 10 working days after the Sponsor first receives notification of the effect.

